4.1 PRE-SCREENING PERIOD

4.1.1. Pre-Screening Visit

Sites are required to pre-screen subjects for study inclusion, evaluating CCR5 positive expression by Immunohistochemistry (IHC) assay prior to performing a full screening visit. This assay will be performed in archival tissue from previous biopsy specimens. If archival tissue is not available then, fresh core or excisional biopsy will be obtained.

The subject will sign and date the pre-screening informed consent form (ICF) prior to any study-related pre-screening procedures. A unique identification number will be assigned to each subject who has provided written pre-screening informed consent.

The subject unique identification number will incorporate a three-digit Study Center number (701, 702 or 703....) and a three-digit numeric ID assigned in successive order of entering the study after signing the pre-screening ICF at each center, beginning with 001 at each site (e.g. 701-001 or 702-001).

Subject Screening # :

XXX - YYY

XXX=Study Center

YYY=Subject Numeric ID

Once the pre-screening ICF has been signed, the following procedures and information will be obtained to confirm pre- eligibility including:

- Review of prior medical records
- CCR5+ expression confirmed by archival or fresh biopsy from primary or metastatic site
- PD-L1 expression confirmed by archival or fresh biopsy from primary or metastatic site

A pre-screening log will be maintained to capture the following information:

- Subject unique identification number
- Patient initials
- Date pre-screened
- Initial eligibility
- Date of re-consent (for the full consent form) or reason for ineligibility

4.2 SCREENING PERIOD

4.2.1. Screening Visit (SV)

The subject (or Legally Acceptable Representative (LAR)) will sign and date the informed consent form (ICF) and Health Insurance Portability Accountability Act (HIPAA) authorization (according to site policy and practices) prior to any study-related procedures.

All study centers will be instructed to maintain the study-specific screening and enrollment logs at their sites. If a subject initially fails to meet inclusion/exclusion criteria and is later reconsidered for participation, the subject will be re-consented and assigned a new unique identification number at the time of re-screening. Subjects who fail their first screening attempt may be re-screened a maximum of once and may be enrolled if they are found to meet all inclusion and no exclusion criteria when re-screened.

Once the Screening ICF has been signed, screening procedures and information will be obtained to confirm subject eligibility including:

- Demographic information and baseline disease characteristics (see [Section 7.3](#)),
- Medical history (see [Section 7.4](#)),
- Prior medications assessment (see [Section 7.5](#)),
- Vital Signs (see [Section 7.6](#)),
- Body Weight & Height measurements (see [Section 7.6](#)),
- Physical examination (see [Section 7.7](#)),
- Eastern Cooperative Oncology Group (ECOG) Performance Review (see [Section 7.8](#))
- 12-lead Electrocardiogram (see [Section 7.9](#))
- Tumor imaging assessment (see [Section 7.15](#))
- Collection of lab specimens (see [Section 7.11](#)) for
 - Complete blood count
 - Biochemistry
 - Serum pregnancy test, for female subjects of childbearing potential.
 - Urine sample for urinalysis parameters

All screening information will be fully documented in the subject's medical records (i.e., source documents).

- For consented subjects who do not meet eligibility criteria, a Screen Failure Case Report Form (CRF) will be completed. The Screen Failure CRF will contain the following details: the subject identification number, the date of ICF signature, demographic information (see

[Section 7.3](#)), and the reason for screen failure. No additional information will be required for subjects who fail screening.

- For consented subjects who meet eligibility criteria, all required screening information will be transcribed onto the appropriate page of the CRF.

4.3 TREATMENT PERIOD

Subjects who meet all eligibility criteria, as per data gathered from Screening Period are to be treated. All subjects who fail to meet eligibility criteria will be considered screen failure and exit the study without further evaluation

Phase Ib

The dose finding portion of study will follow a “3+3” design. The maximum sample size for this portion of the study is 18 subjects that will be followed by treatment according to the schedule described above starting on Cycle 1, Day 1.

Phase II

The maximum sample size for this portion of the study is 30 subjects that will be followed by treatment according to the schedule described above starting on Cycle 1, Day 1.

During the Phase Ib and Phase II of the study, treatment may continue until one of the following criteria applies:

- Disease progression,
- Intercurrent illness that prevents further administration of treatment,
- Unacceptable adverse event(s), or
- Withdrawal of consent

Each treatment cycle consists of 21 days. Leronlimab (PRO 140) will be administered subcutaneously weekly on Days 1, 8, and 15 in combination with carboplatin AUC 5 on Day 1 of each cycle (every 21 days). Day 1 of Cycle 2 begins at Day 22.

4.3.1. Treatment Cycle 1, Day 1

The following assessments will be performed at the first treatment visit of Cycle 1:

- Concomitant medications assessment (see [Section 7.5](#)),
- Vital Signs and body weight measurement (see [Section 7.6](#)),
- Physical examination, including evaluation of all body systems (see [Section 7.7](#))
- ECOG Performance Status (see [Section 7.8](#))

- 12-lead Electrocardiogram (see [Section 7.9](#))
- Collection of lab specimens (see [Section 7.11](#)) for
 - Complete blood count
 - Biochemistry
 - Urine pregnancy test, for female subjects of childbearing potential.
 - Urine sample for urinalysis parameters
 - CTCs PD-L1/CCR5 analysis
 - CTC and CAMLs analysis

Note: Complete blood count, biochemistry and urinalysis can be performed within 3 days prior to each cycle start.

- Leronlimab (PRO 140) Administration (see [Section 6.1.3](#))
- Carboplatin Administration (see [Section 6.2.5](#))
- Post Injection Site Evaluation (performed by Investigator) (see [Section 7.13](#))
- Toxicity assessment (see [Section 7.10](#)) and Review of Adverse Events (see [Section 9](#))

4.3.2. Treatment Cycle 1, Day 8 & Day 15

The following assessments will be performed at during the remaining visits (Day 8 and 15) in the first treatment cycle:

- Concomitant medications assessment (see [Section 7.5](#)),
- Review of Adverse Events (see [Section 9](#))
- Vital Signs (see [Section 7.6](#)),
- Symptom-based physical examination (see [Section 7.7](#))
- Leronlimab (PRO 140) Administration (see [Section 6.1.3](#))
- Post Injection Site Evaluation by Investigator (see [Section 7.13](#))
- Injection Site Pain Assessment (VAS) (see [Section 7.14](#))

4.3.3. Subsequent Treatment Cycle(s), Day 1

The following assessments will be performed at Day 1 of each subsequent treatment cycles:

- Concomitant medications assessment (see [Section 7.5](#)),

- Leronlimab (PRO 140) Administration (see [Section 6.1.3](#))
- Post Injection Site Evaluation by Investigator (see [Section 7.13](#))
- Injection Site Pain Assessment (VAS) (see [Section 7.14](#))

Note: *Vital signs, symptom-based physical examination, post injection site evaluation by Investigator, and injection site pain assessment (VAS) will not be applicable if leronlimab (PRO 140) is self-administered by subjects at home.*

4.4 FOLLOW-UP PERIOD

Duration of Follow Up

- An End of Treatment (EOT) visit will be conducted 30 (\pm 3) days after the last treatment visit (i.e., after last dose of leronlimab (PRO 140) and carboplatin).
- All patients will be followed for adverse events for 30 days after last dose of leronlimab (PRO 140) and Carboplatin, or until the patient starts a new treatment, whichever occurs first.
- Subjects who discontinue treatment for unacceptable adverse event(s) will be followed until resolution or stabilization of the adverse event (i.e. the grade is not changing).
- If a subject stops treatment due to unacceptable adverse event(s) but has not demonstrated disease progression, then the subject will be followed with imaging studies every 9 weeks until the time of progression radiographically according to RECIST v1.1 criteria. In the event that a radiographic response is detected, then this event will be included as a response in the final analysis, and the time of progression used in calculation of the survival analysis.
- Subjects will be followed up by clinic visits or phone call or another method of contact, for survival status every 3 months (\pm 1 month) for 2 years after treatment discontinuation or until death, whichever occurs first.

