
 The number, frequency, and severity of adverse events (AEs) collected from the time of first treatment until 12 weeks after study treatment completion to evaluate safety of leronlimab (PRO 140) and carboplatin in subjects with CCR5+ mTNBC. 
Note: Adverse events will follow National Cancer Institute Common Terminology Criteria for Adverse Events (CTCAE) version 5.0
	

Phase II
 
 PFS according to RECIST v1.1 in participants with Detectable Programmed Death-Ligand 1 (PD-L1) 
Note: The PD-L1 expression testing will be performed at baseline. Breast tissue (primary or metastatic site) collected to analyze for the expression of CCR5 at pre-screening will additionally be used for evaluating PD-L1 expression levels.
 
 Overall response rate (ORR, defined as Complete Response (CR) + Partial Response (PR)), and clinical benefit rate (CBR, defined as CR + PR + Stable Disease (SD)) in subjects with CCR5+ mTNBC treated with leronlimab (PRO 140) and carboplatin. 
Note: Overall response rate is defined as the proportion of patients who achieve an overall response of complete response or partial response in the total number of evaluable patients, assessed by RECIST v1.1. Clinical benefit rate is defined as the proportion of patients who achieve an overall response of complete response or partial response or stable disease in the total number of evaluable patients, assessed by RECIST v1.1. Imaging scans to be done at the end of 2 cycles (i.e., every 6 weeks) for the first 6 cycles (18 weeks) and at the end of 3 cycles (i.e., every 9 weeks) thereafter.
 
 Time to new metastases (TTNM): 
Note: Recorded time from baseline metastatic disease (at time of enrollment) to the time of development of new metastasis in different site. New metastases in same site will be also recorded.
 
 The change from baseline in circulating tumor cells (CTC) level in the peripheral blood. 
Note: Reported unit of measure will be the number of CTCs/milliliter. CTCs enumeration will be performed at baseline and at the time of response assessment. Fraction of baseline positive and change from ≥ 5 CTCs will be recorded and reported.
 
 Overall survival defined as time in months from the date of first study treatment to the date of death; 	

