7.10 TOXICITY ASSESSMENT

Any subject who receives at least one dose of study therapy will be evaluable for toxicity endpoints. Each subject will be assessed for the development of toxicity according to the timeframe referenced in the Schedule of Events table. Toxicity will be assessed according to CTCAE v 5.0 criteria. Refer to [Section 3](#) for the assessment criteria for dose limiting toxicity under Phase Ib of the study. Also

refer to [Table 6-3](#) and [Table 6-4](#) for the dose modification and management of leronlimab (PRO 140) and carboplatin for any toxicity.

All subjects will be followed for adverse events for 30 days after last dose of leronlimab (PRO 140) and carboplatin, or until the subject starts a new treatment, whichever occurs first.

Subjects who discontinue treatment for unacceptable adverse event(s) will be followed until resolution or stabilization of the adverse event (i.e. the grade is not changing). If a subject stops treatment due to unacceptable adverse event(s) but has not demonstrated disease progression, then the subject will be followed with imaging studies every 9 weeks until the time of progression radiographically according to RECIST v1.1 criteria.

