8.7.3. Study Analyses

8.7.3.1 Primary Analysis

The primary analysis will be conducted on the Intent-to-treat (ITT) population.

Primary Outcome (Endpoints) Measures:

Phase Ib

- Maximum Tolerated Dose (MTD) by evaluation of dose-limiting toxicities (DLTs) of leronlimab (PRO 140) when combined with carboplatin AUC5.

Note: The MTD is defined as 1 dose level below the dose in which dose limiting toxicities (DLTs) were observed in ≥ 33% of the participants during Cycle 1.

Phase II

- Progression free survival (PFS) defined as time in months from the date of first study treatment to the date of disease progression or death from any cause, whichever comes first.

Note: All patients who receive at least one dose of leronlimab (PRO 140) and carboplatin combination will be included in the primary analyses of PFS. The Response Evaluation Criteria in Solid Tumors (RECIST v1.1) criteria will be used for objective tumor response assessment (when disease is measurable and non- measurable);

The time in months from start of treatment to progression or death will be measured for all patients who receive at least one dose of study drug. Patients will be followed up to 2 years after completion of treatment.

Secondary Outcome (Endpoints) Measures:

Phase Ib

- The number, frequency, and severity of adverse events (AEs) collected from the time of first treatment until 12 weeks after study treatment completion to evaluate safety of leronlimab (PRO 140) and carboplatin in subjects with CCR5+ mTNBC.

Note: Adverse events will follow National Cancer Institute Common Terminology Criteria for Adverse Events (CTCAE) version 5.0

Phase II

- PFS according to RECIST v1.1 in participants with Detectable Programmed Death-Ligand 1 (PD-L1)

Note: The PD-L1 expression testing will be performed at baseline. Breast tissue (primary or metastatic site) collected to analyze for the presence of CCR5 at pre-screening will additionally be used for evaluating PD-L1 expression levels.

- Overall response rate (ORR, defined as Complete Response (CR) + Partial Response (PR)), and clinical benefit rate (CBR, defined as CR + PR + Stable Disease (SD)) in subjects with CCR5+ mTNBC treated with leronlimab (PRO 140) and carboplatin.

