Note: Overall response rate defined as the proportion of patients who achieve an overall response of complete response or partial response in the total number of evaluable patients, assessed by RECIST v1.1. Clinical benefit rate is defined as the proportion of patients who achieve an overall response of complete response or partial response or stable disease in the total number of evaluable patients, assessed by RECIST v1.1. Imaging scans to be done at the end of 2 cycles (i.e., every 6 weeks) for the first 6 cycles (18 weeks) and at the end of 3 cycles (i.e., every 9 weeks) thereafter.

- Time to new metastases (TTNM);

Note: Recorded time from baseline metastatic disease (at time of enrollment) to the time of development of new metastasis in different site. New metastases in same site will be also recorded.

- The change from baseline in circulating tumor cells (CTC) level in the peripheral blood.

Note: Reported unit of measure will be the number of CTCs/milliliter. CTCs enumeration will be performed at baseline and at the time of response assessment. Fraction of baseline positive and change from ≥ 5 CTCs will be recorded and reported.

- Overall survival defined as time in months from the date of first study treatment to the date of death;

Note: Patients will be followed from the start of treatment until 2 years post-treatment or death, whichever occurs first, and average survival time will be measured.

- The number, frequency, and severity of AEs collected from the time of first treatment until 12 weeks after study treatment completion to evaluate safety of leronlimab (PRO 140) and Carboplatin in subjects with CCR5+ mTNBC.

Exploratory Outcome (Endpoints) Measures:

- Measure immune biomarkers (PD-L1) in CTCs, metastatic tissue and immune cells such as CAMLs and correlate with therapeutic benefit (PFS); and

- Correlation between CCR5 expression (CTCs, CAMLs) and PD- L1 expression.

PFS will be calculated using Kaplan-Meier curves and the median PFS will be read from this curve. Response rates (overall response rate, clinical benefit rate) will be calculated using proportions and 95% confidence intervals. Time to new metastases and overall survival will also be analyzed using Kaplan-Meier curves. Exploratory serial blood markers will be related to PFS using Cox regression, and to response using logistic regression.

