9.2 REPORTING AND FOLLOW-UP OF ADVERSE EVENTS

Report initiation for all AEs and serious adverse events (SAEs), (see [Section 9.3](#)), will begin at the time of the first treatment and continue up to the final study visit. All events will be followed to resolution or until 30 days after the subject completes the study. A final assessment of outcome will be made at that time.

All AEs must be recorded in the subject's medical records and on the CRF. AEs will be reported using customary medical terminology along with the following information: the onset and end dates, whether the event is considered to be a SAE (see [Section 9.3](#)), the impact the event had on study treatment (see [Section 9.2.1](#)), the CTCAE grade (intensity) of the event (see [Section 9.2.2](#)), the causality of the event (see [Section 9.2.3](#)), whether treatment was given as a result of the event (see [Section 9.2.4](#)), and the outcome of the event (see [Section 9.2.5](#)).

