- [21] All subjects will be followed for adverse events for 30 days after last dose of PRO 140 and carboplatin, or until the subject starts a new treatment, whichever occurs first.
- [22] Subjects who discontinue treatment for unacceptable adverse event(s) will be followed until resolution or stabilization of the adverse event (i.e. the grade is not changing). If a subject stops treatment due to unacceptable adverse event(s) but has not demonstrated disease progression, then the subject will be followed with imaging studies every 9 weeks until the time of progression radiographically according to RECIST 1.1 criteria. In the event that a radiographic response is detected, then this event will be included as a response in the final analysis, and the time of progression used in calculation of the survival analysis.
- [23] Limited to all subsequent anti-cancer treatments.

10. APPENDIX 2

[figure not shown]
[figure not shown]

Figure 3-2: 3+3 Study Design

Note: A standard "3+3" dose escalation design starting at dose \mathcal{K} . The maximum tolerated dose (MTD) is the highest dose at which 0 or 1 dose-limiting toxicities (DLTs) are observed in six subjects. If de-escalation occurs at the first dose level, the study is discontinued.

11. APPENDIX 3

Figure 4-1: Study Flow Diagram

12. APPENDIX 4

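### The adverse event windows conflict (12 weeks, 30 days or next treatment, an undefined final visit); under the 30-day rule about 54 of the 84 post-treatment endpoint days have no routine collection

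*Protocol*

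**What the plan says.** **Endpoint.** The Protocol synopsis defines the Phase Ib safety outcome as "The number, frequency, and severity of adverse events (AEs) collected from the time of first treatment until 12 weeks after study treatment completion". Protocol 8.7.3.1 words the Phase II outcome the same way: "The number, frequency, and severity of AEs collected from the time of first treatment until 12 weeks after study treatment completion". SAP 2.4.2 repeats the 12-week limit for both phases.

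**Follow-up rule.** Protocol 4.4 states "All patients will be followed for adverse events for 30 days after last dose of leronlimab (PRO 140) and Carboplatin". The same sentence closes follow-up sooner for anyone who moves to another therapy within that time. Protocol 7.10 repeats it ("All subjects will be followed for adverse events for 30 days after last dose of leronlimab (PRO 140) and carboplatin"), as does footnote 22 of the Protocol's schedule of assessments. The SAP's own schedule (Appendix 1, footnote 21) agrees: "All subjects will be followed for adverse events for 30 days after last dose of PRO 140 and carboplatin". In that schedule the Adverse Events row is marked up to the End of Treatment (EOT) visit and is blank at survival follow-up.

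**Reporting rule.** Under Protocol 9.2, reporting of AEs and SAEs "will begin at the time of the first treatment and continue up to the final study visit". That visit is not defined. Protocol 9.4 ties SAE reporting to the same period.

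**Survival contacts.** Protocol 4.4.2 lists a toxicity assessment at these contacts. The note beneath it concerns subjects who stopped for an unacceptable AE. Footnote 22 of the SAP schedule describes the same group.

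**TEAE definition.** Protocol 8.7.3.2 and SAP 8.4.1 count events from first treatment onward and give no end date.

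**The concern.** A secondary endpoint in both phases is defined over a period that the follow-up rule does not cover, and no section says which rule takes precedence. A site working from Section 4.4 and the schedule would stop routine AE collection at about day 30. A site working from Section 9.2 might continue for much longer. Late events could then be missed or captured unevenly, and the open-ended TEAE definition would tabulate whatever happened to be recorded. A reader of the final table would take it to describe 12 weeks after treatment, when for many subjects it might describe 30 days or less. Because SAE reporting borrows its period from Section 9.2, the ambiguity also reaches SAEs.

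**Working it through.** The documents give no figure for this gap, so there is nothing to reproduce. The check is day arithmetic, taking completion of study treatment to be the last dose of both drugs.

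**Inputs**
- Endpoint window: 12 weeks (Protocol synopsis and 8.7.3.1; SAP 2.4.2).
- AE follow-up: 30 days, or start of new treatment if earlier (Protocol 4.4, 7.10; SAP Appendix 1, footnote 21).
- EOT visit: day 30 ± 3 (Protocol 4.4.1).
- Survival contacts: every 3 months ± 1 month for 2 years (Protocol 4.4.2).
- Study completion: end of survival follow-up, up to 2 years after treatment discontinuation, or death (Protocol Section 5).

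**Formulas**
- Endpoint window = 12 × 7 = 84 days.
- Uncovered days = 84 - min(30, day new treatment starts).

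**If the 30-day rule governs**
- No new treatment by day 30: 84 - 30 = 54 days; 54/84 = 64.3%.
- If collection ends at an EOT visit held on day 27: 84 - 27 = 57 days (67.9%). On day 33: 84 - 33 = 51 days (60.7%).
- New treatment on day 21: 84 - 21 = 63 days (75.0%).
- New treatment on day 14: 84 - 14 = 70 days (83.3%).
- New treatment on day 7: 84 - 7 = 77 days (91.7%).

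**If Section 9.2 governs**
- Final study visit read as the last survival contact: for a subject followed through that contact, 0 of the 84 days fall outside the reporting window, which then runs up to about 2 years.
- Final study visit read as EOT: the gap is again about 54 days.
- Neither reading gives 12 weeks.

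**Is there a contact that could close the gap?** With a month of 365.25/12 = 30.4 days, the first survival contact is due at about day 91, with a window of about day 61 (2 months) to day 122 (4 months). It can therefore fall before day 84. No visit is fixed between EOT and day 84.

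**The case against.** The strongest reply is that Section 9.2 is the section on AE reporting and already requires AEs and SAEs to be reported to the final study visit. Read with the definition of study completion in Section 5, that could mean the last survival contact, in which case no endpoint day is uncovered. A toxicity item is also planned at survival contacts. And safety is analysed descriptively on observed data (SAP 7.3 and 8.4), so AE counts can be tabulated whatever the cut-off.

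Much of this stands, and it rules out two stronger readings. A reader might infer that 54 days go uncollected whatever rule applies. The documents do not support that: it depends on the 30-day rule governing, and subjects who stopped for an unacceptable AE have toxicity follow-up beyond EOT. A reader might also infer that the endpoint cannot be computed. It can be tabulated; what is unsettled is the period that the table covers.

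The reply does not remove the conflict. Section 9.2 contradicts Sections 4.4 and 7.10 without overriding them, and its end point is undefined. The toxicity item at survival contacts carries a note about one group only, and the SAP schedule marks no AE collection there. A subject who stops for progression has no scheduled AE review between EOT and day 84 under those provisions.

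**Conclusion.** The inconsistency is real and lies in current text: three limits for AE collection and a TEAE definition that chooses none of them. If the 30-day rule and the SAP schedule govern, about 54 of 84 post-treatment endpoint days (64%) lack routine AE collection. The range is 51 to 57 days across the EOT visit window, and the gap is larger when new treatment starts before day 30. The stated 12-week endpoint is then not delivered. If Section 9.2 runs to the last survival contact, the gap is zero but the window is far longer than the endpoint's.

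This rests on two assumptions: that treatment completion means the last dose of both drugs, and that the marks in the SAP schedule reflect the intended collection.

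A reader might infer that dose finding is compromised. It is not: dose-limiting toxicities are assessed in Cycle 1, so the Phase Ib MTD does not depend on the post-treatment window.

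**What to change.** Adopt one AE window and state it identically in the Protocol synopsis, 4.4, 4.4.2, 7.10, 8.7.3.1, 9.2 and schedule, and in SAP 2.4.2 and Appendix 1. Define the final study visit in Section 9.2. Give the TEAE definition (Protocol 8.7.3.2, SAP 8.4.1) an end date that matches. There are two ways to do it:

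1. **Restate the endpoint to match the AE collection actually planned.** Set out the SAE reporting period separately, because Protocol 9.4 takes it from Section 9.2 and it would otherwise be shortened by default. The cost is a shorter stated safety window. If the window still closes at new treatment, time at risk will differ between subjects and should be reported.
2. **Keep 12 weeks.** Have an existing follow-up contact made on or after day 84 collect AEs for all subjects back to EOT. The present window of the first contact opens at about day 61, so the wording must guarantee that the contact used is not earlier than day 84. State also whether events after the start of new treatment count. The cost is AE questions added to one existing contact; no new visit is needed.

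Either option is a wording change to the Protocol and SAP.
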